#### 11.1.4 Response Criteria

##### 11.1.4.1 Evaluation of Target Lesions

Prior to the first PD assessment, patients will be evaluated according to the following RECISTv1.1 response:

Complete Response (CR): Disappearance of all target lesions, determined by two separate observations conducted not less than 4 weeks apart. There can be no appearance of new\* lesions.

Partial Response (PR): At least a 30% decrease in the sum of the diameters of target lesions, taking as reference the baseline sum diameters. There can be no appearance

of new\* lesions.

**Progressive Disease (PD):** At least a 20% increase in the sum of the LD of target lesions (with a minimum absolute increase of 5 mm), taking as reference the smallest sum LD recorded since the treatment started, or the appearance of one or more new\* lesions.

**Stable Disease (SD):** Neither sufficient shrinkage to qualify for PR (taking as reference the baseline sum LD) nor sufficient increase to qualify for PD (taking as reference the smallest sum LD since the treatment started).

**For patients receiving atezolizumab only:**

After the first PD assessment per RECISTv1.1 (=iUPD per iRECIST), patients will be evaluated for iCPD 4-8 weeks later according to the following definition:

**Immune Unconfirmed Progressive Disease (iUPD):** At least a 20% increase in the sum of the LD of target lesions (with a minimum absolute increase of 5 mm), taking as reference the smallest sum LD recorded since the treatment started, or appearance of new\* lesions since the last evaluation.

**Immune Confirmed Progressive Disease (iCPD):** If iUPD was assigned based on increase in size of target or non-target lesions, iCPD is assigned if a further increase in size of lesions is observed or if new lesions appear. If iUPD was assigned based only on the development of new lesions, iCPD is only assigned if at next assessment additional new lesions appear or an increase in size of new lesions is seen ( $\geq 5$  mm for sum of new lesion target or any increase in new lesion non-target).

\*excludes skeletal lesions

#### 11.1.4.2 Evaluation of Non-Target Lesions

**Complete Response (CR):** Disappearance of all non-target lesions and normalization of tumor marker level. All lymph nodes should be non-pathological in size (<10 mm short axis).

**Incomplete Response/Stable Disease (SD):** Persistence of one or more non-target lesion(s) and/or maintenance of tumor marker level above the normal limits.

**Progressive Disease (PD):** Appearance of one or more new lesions and/or unequivocal progression of existing non-target lesions.

Although a clear progression on non-target lesions in absence of stable target lesions is exceptional, the opinion of the treating physician should prevail in such circumstances.

#### 11.1.4.3 Evaluation of New Lesions

The finding of a new lesion should be unequivocal (i.e. not due to difference in scanning technique, imaging modality, or findings thought to represent something other than tumor (for example, some ‘new’ bone lesions may be simply healing or flare of pre-existing lesions). However, a lesion identified on a follow-up scan in an anatomical location that was not scanned at baseline is considered new and will indicate PD. If a new lesion is equivocal (because of small size etc.), follow-up evaluation will clarify if it truly represents new disease and if PD is confirmed, progression should be declared using the date of the initial scan on which the lesion was discovered.

#### 11.1.4.4 Evaluation of Best Overall Response

The best overall response is the best response recorded from the start of the treatment until disease progression/recurrence (taking as reference for progressive disease the smallest measurements recorded since the treatment started). The patient's best response assignment will depend on the achievement of both measurement and confirmation criteria.

### **11.1.5 Safety/Tolerability**

Analyses will be performed for all patients having received at least one dose of study drug. The study will use the CTCAE version 5.0 for reporting of adverse events (<http://ctep.cancer.gov/reporting/ctc.html>).

### **11.1.7 Objective Response Rate (ORR)**

ORR will be defined as the proportion of subjects who experience radiographic response (complete response or partial response) by RECIST 1.1 criteria OR PSA response.

[figure not shown]
Per PCWG3 criteria, PSA response is defined by at least 50% decline in PSA level from baseline measured twice at least 3 weeks apart. Based on PCWG3 criteria, a favorable effect on PSA may be delayed for  $\geq 12$  weeks. PSA will be monitored every 3 weeks, but early rises in PSA before 12 weeks will not be considered when determining PSA response, i.e. PSA response will be determined in relation to baseline even if PSA initially rises after starting on trial therapy.

### **11.1.8 Criteria for PSA Progression**

For rising PSA after an initial decline from baseline, the PSA is recorded from the start of therapy to first PSA increase that is  $\geq 25\%$  and  $\geq 2\text{ng/mL}$  above the nadir, which is confirmed by a second value 4 or more weeks later, confirming a rising trend. If there is no initial decline from

baseline, PSA progression is defined as  $\geq 25\%$  increase and  $\geq 2$  ng/mL increase from baseline **beyond 12 weeks**.

Patients who have only documented PSA progression in the absence of radiographic or clinical progression should continue on study therapy.

### 11.1.9 Duration of Response

**Duration of overall response:** The duration of overall response is measured from the time measurement criteria are met for PSA or radiographic response until the first date that PCWG3 progression is documented, or if there is interval development of recurrent or progressive disease based on clinical, soft tissue or bone scan progression by PCWG3 criteria.

## 11.2 Radiographic Disease Criteria

All radiographic response criteria are as per PCWG3 criteria summarized below.

### 11.2.1 Nodal Disease

Up to five (5) lesions are recorded per site of disease. These will be assessed as per RECIST 1.1 with the following PCWG3 caveats:

1. Changes in size are recorded using a waterfall plot
2. Favorable change is confirmed with a second scan
3. Complete elimination of disease at any site is recorded separately
4. Only changes in lymph nodes that were  $\geq 15$  mm in the short axis are reported
5. Changes in pelvic (regional) nodes versus extrapelvic (distant/metastatic) nodes are recorded separately

### 11.2.2 Visceral Disease

Visceral disease includes lesions in lung, liver, adrenal, and CNS sites. These will be assessed as per RECIST 1.1 with the following PCWG3 caveats:

1. Changes in liver, lung, adrenal, and CNS sites are recorded separately
2. Only changes in lesions  $\geq 1.0$  cm in the longest dimension are reported

### 11.2.3 Bone Disease

Bone disease is evaluated as per PCWG3 criteria, with changes recorded as improved or stable (no new lesions) or worse (new lesions). Additional PCWG3 caveats include:

1. Changes in intensity of uptake alone do not constitute progression or regression
2. No new lesions: continue therapy in absence of other signs of progression
3. New lesions (progression) is defined by the following per PCWG3:
  - a. Exclude pseudoprogression in the absence of symptoms or other signs of progression
  - b. At least two new lesions on first post-treatment scan, with at least two additional lesions on the next scan (2+2 rule)
  - c. If at least two additional new lesions are seen on the next (confirmatory) scan, the date of progression is the date of the first post-treatment scan, when the first two new lesions were documented
  - d. For scans after the first post-treatment scan, at least two new lesions relative to the first post-treatment scan confirmed on a subsequent scan

## 12. DATA REPORTING / REGULATORY REQUIREMENTS

Adverse event lists, guidelines, and instructions for AE reporting can be found in Section 7.0 (Adverse Events: List and Reporting Requirements).

### 12.1 Data Reporting

#### 12.1.1 Method

The DF/HCC Office of Data Quality (ODQ) will collect, manage, and perform quality checks on the data for this study.

#### 12.1.2 Responsibility for Data Submission

Investigative sites are responsible for submitting data and/or data forms to the Office of Data Quality (ODQ) in accordance with DF/HCC policies.

### 12.2 Data Safety Monitoring

The DF/HCC Data and Safety Monitoring Board (DSMB) will review and monitor study progress, toxicity, safety and other data from this study. The Board is chaired by a medical oncologist from outside of DF/HCC and its membership composed of internal and external institutional representation. Information that raises any questions about participant safety or

protocol performance will be addressed by the Sponsor-Investigator, statistician and study team. Should any major concerns arise, the DSMB will offer recommendations regarding whether or not to suspend the study.

The DSMB will meet twice a year to review accrual, toxicity, response and reporting information. Information to be provided to the DSMB may include: participant accrual; treatment regimen information; all adverse events and serious adverse events reported across all sites by category; summary of any deaths on study; audit results; and a summary provided by the study team. Other information (e.g. scans, laboratory values) will be provided upon request.

### **12.3 Multi-Center Guidelines**

This protocol will adhere to DF/HCC Policy MULTI-100 and the requirements of the DF/HCC Multi-Center Data and Safety Monitoring Plan. The specific responsibilities of the Sponsor-Investigator, Coordinating Center, and Participating Institutions and the procedures for auditing are presented in Appendix B.

## **13. STATISTICAL CONSIDERATIONS**

### **13.1 Study Design/Endpoints**

#### **13.1.1 Primary Endpoints**

- Co-primary endpoints for efficacy are 6-month progression free survival (PFS) rate and objective response rate (ORR).
  - PFS is defined as the duration of time from the start of treatment to disease progression (as defined by PCWG3 criteria), or death, whichever occurs first (for detailed definition please see Section 11.1.6).
  - ORR is the proportion of evaluable patients who had radiographic response (complete response or partial response) by RECIST 1.1 criteria OR 50% decline in PSA from pretreatment baseline per PCWG3 criteria (for detailed definition please see Section 11.1.7).
- Primary endpoint for dose safety for abemaciclib cohort Arm C (for detailed definition please see Section 7.3).

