Statistical Methodology	
Efficacy Analysis
 
27 total evaluable patients in Arm A will provide 86% power for 6 month progression-free survival (with null 6m-PFS 12% and alternative of 34%) and 85% power for objective response rate (with null ORR 10% and alternative of 30%) and with a one-sided type 1 error of 8%. When 12 patients in Arm A have been enrolled and followed for maximum 6 months, Arm A will close if there is no patient with response or with 6m-PFS. Otherwise, the 2nd stage will open, and 15 more patients will be enrolled in that arm for 8 months for a total of 27 patients. The 6m-PFS Kaplan-Meier estimate for Arm A will be reported with a 90% confidence interval. If 6 patients experience 6m-PFS or 5 patients have an objective response by the end of stage 2, this study would suggest meaningful clinical activity.
 
For Arm C (CDK12 loss CRPC), similar assumptions will be made with expected efficacy with a null 6m-PFS rate of 12% and an alternative response of 34% or greater with abemaciclib therapy. Due to accrual limitations in this arm, we will use a single stage design. Five patients with CDK12 loss will be accrued to an atezolizumab monotherapy as exploratory group. Then, 16 additional subjects with CDK12 loss will be accrued to therapy with abemaciclib for 18 months, the same accrual time as arm A. A one-sided, one-sample log-rank test calculated from a sample of 16 subjects achieves 80-85% power at a 0.05 significance level to detect 22% of difference in 6m-PFS. Follow-up continues for 12 months after the last subject is added. The 6m-PFS Kaplan-Meier estimate will be reported with a 90% confidence interval.
 
Safety analysis
 
Safety and tolerability for abemaciclib monotherapy and for the combination of abemaciclib and atezolizumab will be summarized by rate of dose-limiting toxicities (DLTs) as defined in section 8.3.8 using percentage and 90% confidence interval, and by incidence and grade of adverse events (AEs) by CTCAE version 5.0.
 
Bayesian toxicity monitoring was planned to be used for all patients enrolled to Arm B and to the combination treatment cohort of Arm C (up to a maximum of 43 patients). If the rate of patients experiencing dose limiting toxicities (DLTs) at the starting dose exceeded the pre-specified threshold for excessive toxicity, then subsequent patients randomized to

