### **3. PARTICIPANT SELECTION**

#### **3.1 Eligibility Criteria**

- 3.1.1 Diagnosis of metastatic castration resistant prostate cancer (mCRPC), with histologic confirmation of adenocarcinoma of the prostate (without evidence of small cell carcinoma), with progressive disease at the time of study entry by either
  - Sequence of at least 2 rising PSA values at a minimum of 1-week intervals
  - Radiographic progression per RECIST1.1 for soft tissue and/or per PCWG3 (81) for bone, with or without PSA progression
- 3.1.2 Adult males 18 years of age or older.
- 3.1.3 ECOG performance status of 0 or 1
- 3.1.4 Patients must have metastatic disease by bone scintigraphy or other nodal or visceral lesions on CT or MRI with a bone or soft tissue lesion amenable to image-guided percutaneous biopsy at acceptable risk for research biopsy per institutional standards, and the patient must be evaluable for disease response by either
  - Baseline PSA  $\geq$  2.0 ng/mL OR
  - Measurable disease per RECIST 1.1

- 3.1.5 Past progression or intolerance to at least one novel antiandrogen therapy (abiraterone, enzalutamide, galeterone, apalutamide, darolutamide, orteronel, seviteronel or equivalent) in either the hormone-sensitive or castration-resistant disease setting.
- 3.1.6 Not a candidate for docetaxel or cabazitaxel chemotherapy due to:
- progression within 12 months of completion or intolerance to prior taxane OR
  - refusal of taxane OR
  - contraindication to, or lack of fitness for taxane OR
  - Investigator assessment that taxane is not clinically indicated or preferred.
- 3.1.7 Maintenance of castration status, defined as serum testosterone level of less than 50 ng/dL. Patients must be surgically castrate or maintained on LHRH agonist or antagonist therapy for the duration of the study period.
- 3.1.8 Must have recovered from any treatment-related toxicities to  $\leq$  CTCAE grade 1.
- Patients with  $\leq$  CTCAE grade 2 anorexia, alopecia, neuropathy, and/or fatigue however, are also permitted to enroll.
- 3.1.9 Participants must have adequate organ and marrow function as defined below:
- leukocytes  $\geq 3,000/\text{mcL}$
  - absolute neutrophil count  $\geq 1,500/\text{mcL}$
  - lymphocyte count  $\geq 500/\text{mcL}$
  - hemoglobin  $\geq 9 \text{ g/dL}$  (without transfusion or growth factor in prior 28 days, except for patients assigned to atezolizumab monotherapy in Arm C for whom transfusion to meet this eligibility criterion is permitted)

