## **5.7 Patient Replacement**

Patients who have been registered and receive no protocol therapy will be replaced.

Patients who receive local intervention (e.g., palliative radiation) may be considered not evaluable. These patients may subsequently be assigned a conservative censoring or progression date.

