#### 11.1.1 Definitions

Evaluable for Target Disease response. Only those participants who have measurable disease present at baseline, have received at least one cycle of therapy, and have had their disease re-evaluated will be considered evaluable for target disease response. These participants will have their response classified according to the definitions stated below. (Note: Participants who exhibit objective disease progression prior to the end of cycle 1 will also be considered evaluable.)

Evaluable Non-Target Disease Response. Participants who have lesions present at baseline that are evaluable but do not meet the definitions of measurable disease, have received at least one cycle of therapy, and have had their disease re-evaluated will be considered evaluable for non-target disease. The response assessment is based on the presence, absence, or unequivocal progression of the lesions.

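### The co-primary ORR has two stated denominators and no efficacy set; on one reading, treated patients who are never re-evaluated drop out and the reported rate rises

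*Combined protocol and SAP*

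**What the plan says.** Section 13.1.1 gives the co-primary ORR as follows: "ORR is the proportion of evaluable patients who had radiographic response" by RECIST 1.1, or who had a 50% PSA decline. It refers to Section 11.1.7 for the detailed definition, which reads: "ORR will be defined as the proportion of subjects who experience radiographic response", or PSA response. The clinical benefit rate (CBR) in Sections 13.1.2 and 13.4 also uses evaluable patients. Section 13.3 defines a safety set (at least one dose), but Section 13 names no efficacy set.

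Evaluability appears in three other places:

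- **Section 11.1.1**, for target disease, admits patients with measurable disease at baseline who "have received at least one cycle of therapy, and have had their disease re-evaluated will be considered evaluable for target disease response". A note adds: "Participants who exhibit objective disease progression prior to the end of cycle 1 will also be considered evaluable". The non-target definition also requires one cycle and a re-evaluation. Neither definition covers PSA.
- **Section 3.1.4** makes it an entry condition: "the patient must be evaluable for disease response by either" baseline PSA of at least 2.0 ng/mL or measurable disease.
- **Section 5.7** says: "Patients who receive local intervention (e.g., palliative radiation) may be considered not evaluable". On replacement it says only: "Patients who have been registered and receive no protocol therapy will be replaced".

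The Synopsis states the sample size as "27 total evaluable patients in Arm A will provide 86% power" for 6-month PFS. Section 13.2 counts 27 patients accrued, and Section 13.3 caps Arm A at 27 enrolled.

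**The concern.** A co-primary endpoint in a single-arm comparison with a fixed 10% null needs one denominator, fixed before outcomes are known. Here the text supports two. One of them depends on what happens after treatment starts, and Section 5.7 leaves some exclusions to judgement in an open-label trial.

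Under Section 11.1.1 the treated patients who can be lost are those who die early, stop for toxicity, withdraw or decline clinically without a scan, and possibly those given local treatment. The first on-treatment imaging falls at cycle 4 day 1, about nine weeks in, and Table 27 schedules none at the end-of-treatment visit. Most patients lost this way will be non-responders, so removing them raises ORR and CBR. The other co-primary endpoint, 6-month PFS, runs from the start of treatment and counts deaths, so the two endpoints could rest on different patients.

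**Working it through.** **Inputs.** Arm A has 12 + 15 = 27 patients. The ORR null is 10% and the alternative 30%. Activity is declared at 5 responses or 6 patients progression-free at 6 months (Synopsis, Section 13.2). ORR is reported with a 90% binomial interval (Section 13.2). The number of treated patients who would not be evaluable is not given. I assume m = 0 to 7 of 27, all non-responders.

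**Plan's own figures.** Section 13.2 states 85% power for ORR, 86% for 6-month PFS, one-sided alpha 0.08 and 37% early stopping. An exact two-stage calculation with independent endpoints returns 84.7%, 85.7%, 0.077 and 37.5%, but only with every cut-off one patient higher than printed. The printed cut-offs give 94.5%, 94.4%, 0.210 and 6.1%. That is a separate matter. Both calculations use 27 patients and counts, so the denominator chosen for reporting does not enter them.

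**Effect on the reported rate.** ORR = 5/(27 − m), with Clopper-Pearson 90% limits: the lower is the 5th percentile of Beta(5, 27 − m − 4), the upper the 95th percentile of Beta(6, 27 − m − 5).

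| Dropped (m) | Denominator | ORR | 90% CI |
|---|---|---|---|
| 0 | 27 | 18.5% | 7.6 to 35.1 |
| 2 | 25 | 20.0% | 8.2 to 37.5 |
| 3 | 24 | 20.8% | 8.6 to 38.9 |
| 4 | 23 | 21.7% | 9.0 to 40.4 |
| 5 | 22 | 22.7% | 9.4 to 42.0 |
| 7 | 20 | 25.0% | 10.4 to 45.6 |

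The inflation is 21.7 − 18.5 = 3.2 points for four dropped and 25.0 − 18.5 = 6.5 points for seven. With five responders the lower limit exceeds 10% only when the denominator falls to 20. At 21 to 27 it takes six responders.

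**Effect on the decision.** The rule compares a count with 5. Among 27 enrolled, relabelling m non-responders as not evaluable leaves the count as it was.

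**Power.** P(X ≥ 5) at a 30% rate is 0.941 for n = 27 and 0.864 for n = 23, which might look like a loss. But if 30% is the rate among all treated patients and the four dropped are non-responders, the rate among the other 23 is 0.30 × 27/23 = 35.2%, and P(X ≥ 5 of 23) = 0.947.

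**The case against.** The strongest reply is that evaluable in Section 13.1.1 may mean no more than it does in Section 3.1.4. That is the only place where the word is attached to both arms of the composite, PSA or measurable disease. Every eligible patient then qualifies, 27 evaluable agrees with 27 accrued, and nothing is inflated. This reading is open, but no text selects it over Section 11.1.1, which is the only definition of evaluability stated in terms of follow-up.

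The losses under Section 11.1.1 are also narrower than its one-cycle rule suggests. The note quoted above keeps objective progression before the end of cycle 1. Table 27 (note 3) and Section 5.5 continue scans or PSA after a stop for reasons other than progression, and Section 11.1.4.4 asks for progression to be documented after symptomatic deterioration. So many toxicity stops will still be re-evaluated. Those left are early deaths, withdrawals, patients who start new treatment before a scan, and some who stop within one cycle.

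A reader might go further and infer three things that the documents do not support:

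- **All early failures are excluded.** The cycle 1 note says otherwise.
- **The trial loses power.** The drop from 94% to 86% appears only if 30% is applied unchanged to the 23 who remain. In that case the chance is 86% whatever the denominator is called.
- **The type I error rises.** That would need accrual to continue to 27 evaluable patients. With 3 non-evaluable per 27 treated, the single-stage P(X ≥ 5) under the null would go from 0.127 to 0.181. Section 5.7 replaces only patients who received no therapy, and Section 13.3 caps Arm A at 27 enrolled.

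**Conclusion.** The two definitions conflict in current text, and no efficacy set resolves them. On the Section 11.1.1 reading the reported ORR and CBR are biased upwards; on the Section 3.1.4 reading they are not. For five responders the bias in ORR runs from 0 to 6.5 points over an assumed 0 to 7 non-responders dropped. With up to six dropped, the 90% interval still contains the 10% null; at seven it does not. The size rests on that assumed range and on all those dropped being non-responders. The Arm A go/no-go result with 27 enrolled is unaffected, and no loss of power follows. This should be settled before analysis because it decides how a co-primary result is reported.

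**What to change.** 1. In the Synopsis and Sections 11.1.7, 13.1.1, 13.1.2 and 13.4, define the ORR and CBR denominator as all patients who received at least one dose, and count a patient with no post-baseline assessment as a non-responder (for CBR, as no benefit).
2. In Section 5.7, state that patients given local intervention stay in this denominator.
3. In the Synopsis, describe the Arm A sample as 27 treated patients in place of 27 evaluable ones.
4. Report ORR in the Section 11.1.1 evaluable set only as a sensitivity analysis, and say how patients assessed by PSA alone enter that set.

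The cost is an amendment to wording in the protocol and its Synopsis, with no added patients or procedures. The reported ORR and CBR may be slightly lower.
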